- (2) The behavior and experience of the mobilizing professionals will be evaluated using episodic interviews as well as standardized observations. Nurses with specialized training in anesthesia and intensive care, nurses and physiotherapists who have at least three years of professional experience in an intensive care unit as well as medical specialists who have completed their training as medical specialists or who have a leading position in an intensive care unit are included. In addition, the individuals have an employment contract at LMU Klinikum. Furthermore, the secondment to the anesthesiological intensive care units is an inclusion criterion.
- (3) The effects on patient outcomes, primarily duration of ventilation, muscle mass (sonographic examination) and physical activity (measured by established scores such as FSS-ICU and MRC classification), will be measured at different points in time and compared with a historical patient population. Secondary outcomes such as delirium incidence, hemodynamic parameters, respiratory parameters but also longitudinal parameters such as intensive care and hospital length of stay will be analyzed from routine data/patient records. Included are informed consenting patients who will undergo a planned surgical procedure that involves postoperative intensive treatment and an anticipated duration of ventilation of more than 48 hours. These patients will receive standardized early mobilization using the robotic system at either ten frequencies or for seven days. No invasive procedures such as blood sampling will be performed as part of the study. To evaluate the effect of robot-assisted VEM, the outcomes

will be compared with a historical comparison group. Approximately 30 patients shall be included. The results will be compared to a historical group (n=30) with conventional early mobilization.

The intervention is planned for a duration of five to six months starting in August 2021.

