## 4.3 EVALUATION OF THE EFFECTS ON PATIENT OUTCOMES

- Can robot-assisted early mobilization improve muscle strength and reduce muscle loss compared with the historical collective?
- Can robot-assisted early mobilization reduce the duration of ventilation?  
In addition, further questions will be addressed:
- Does robotic-assisted early mobilization result in changes in consciousness, pain, cognition, health perception, cardiocirculatory and respiratory function, other factors such as pressure ulcers, bowel emptying, insulin requirements, and duration of treatment?

For this purpose, the following outcome criteria of the patients are examined.

Primary outcome criteria	Physical function/muscle strength	Surveyed according to the MRC (Medical Research Council) classification on upper and lower extremity and using the FSS-ICU (32, 33) at discharge ICU.
	Parameters for the assessment of muscle deterioration	Muscle thickness of quadriceps femoris muscle (thickness quadriceps femoris muscle and cross sectional area rectus femoris muscle)  Muscle thickness of the diaphragm / Thickening fraction diaphragm  Diaphragm mobility at discharge ICU
	Ventilation time	Duration (d) of invasive ventilation

Secondary outcome criteria	Consciousness/ cognition/ pain/ health perception	Pain using the Visual Analog Scale (VAS) (before and after mobilization).  Delirium incidence using the CAM ICU (34): number of days without delirium.  Sedation level using the Richmond Agitation Sedation Scale (RASS)(35)  level of consciousness using the Glasgow Coma Scale (GCS) (36)  Health-related quality of life after 3 months using the SF-36 questionnaire (37)
	Hemodynamics	Blood pressure / catecholamine demand / heart rate / cardiac output / oxygen consumption
	Respiration	CPAx-respiratory function(38) / oxygenation index / lung ultrasound parameter
	Others	Intestinal evacuation (yes/no)  Decubitus (grade classification 1-4 according to Shea (39))  Lactate level before and after mobilization (if laboratory value available)  Insulin requirement
	ICU Scores	SOFA [39] / Apache II (40) / SAPS II (41)  Intensive care unit treatment duration / inpatient treatment duration

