## 6. STUDY DESIGN

The present study is a monocentric, prospective intervention study, designed to

- evaluate the feasibility and integration in the setting of an Intensive Care Unit.
- evaluate the behavior and experience of the mobilizing specialists of the robot-assisted VEM in a longitudinal section (three data collection points).
- compare robot-assisted VEM in critically ill intensive care patients with non-robot-assisted early mobilization according to the standard of care of a historical patient population.

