### 7.3. NUMBER OF PATIENTS

In order to test correlations using multiple-variate models (multiple linear regressions) with a statistical power of 80% on approximately 8 independent variables (UV) compared to the dependent variable (AV), an approximate total sample size of 50 subjects is required.

Thus, with an expected drop-out of 10%, 55 patients (robotic intervention and historical comparison group) should be included in the study. A sample size of 20 subjects is considered a lower limit with moderately strong associations between UVs and AV and inclusion of a maximum of 5 UVs, with  $\alpha=5\%$  and  $\text{power}=80\%$  (43, 44). In this regard, if 30-35 patients are included in the robot-assisted intervention and a maximum of 6 UVs, meaningful results can be expected to be obtained in a manageable period of time.

All patients will be included in the intervention only if written informed consent is obtained. Due to the expected patients' recruitment (6-8 patients/month) with a given number of cases (30-35 patients in the intervention), the study is expected to last five to six months from the start. The recruitment rate depends on the number of patients.

In general, all patients meeting the above-mentioned criteria will be included in the study. The study is completed as soon as the required number of patients has been recruited for the intervention. The corresponding number of cases for the historical group will be taken from the routine data.

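### Section 7.3 and the summary give different totals (55, 60, 60 to 70), and the 80% power is tied to no robot-versus-historical difference

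*Protocol*

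**What the plan says.** Protocol Section 7.3 starts from a multiple linear regression with about 8 independent variables and 80% power, for which "an approximate total sample size of 50 subjects is required". It adds 10% for drop-out and concludes that "55 patients (robotic intervention and historical comparison group) should be included in the study".

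The section then gives two further figures. One is a floor: "A sample size of 20 subjects is considered a lower limit with moderately strong associations between UVs and AV", with at most 5 independent variables, 5% alpha and 80% power. The other is the recruitment target, where useful results are expected "if 30-35 patients are included in the robot-assisted intervention and a maximum of 6 UVs". For the controls it says only: "The corresponding number of cases for the historical group will be taken from the routine data".

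The executive summary (Section 1) says: "Approximately 30 patients shall be included. The results will be compared to a historical group (n=30) with conventional early mobilization".

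On purpose, Section 3 puts feasibility first. The group comparison is one of the three aims listed in Section 6: "compare robot-assisted VEM in critically ill intensive care patients with non-robot-assisted early mobilization". Section 4.3 asks: "Can robot-assisted early mobilization improve muscle strength and reduce muscle loss compared with the historical collective"? No section gives an expected or detectable difference between the groups, an SD, an R² or an f² for any primary outcome.

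**The concern.** There are two problems, both within what the protocol itself states.

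First, the totals do not agree. The historical cases are picked retrospectively from routine records. If their number is not fixed by one figure, it can be settled after the robot patients' results are known.

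Second, the sample-size argument concerns associations in a regression, with no effect size attached to the 50. The 80% power therefore says nothing explicit about robot versus historical care. A reader of a non-significant comparison would not know that the study had less than an even chance, or little better, of finding a half-SD difference.

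**Working it through.** **Inputs from the protocol.** Section 7.3: total of 50, about 8 independent variables, 80% power, 10% drop-out, total of 55, 30 to 35 robot patients, floor of 20 with 5 variables. Section 1: about 30 robot and 30 historical patients. Section 7.3 attaches the 5% alpha only to the floor of 20 and does not state sidedness. I assume two-sided 5% throughout.

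**Step 1: the plan's own figure.** 50 × 1.10 = 55. Dividing instead gives 50 / 0.90 = 55.6, or 56. The 55 reproduces, so the inflation step is not an arithmetic error.

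**Step 2: the totals side by side.**

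- Section 7.3, stated total: 55.
- Section 7.3, robot target plus an equal historical group: 30 + 30 = 60 to 35 + 35 = 70.
- Section 1: 30 + 30 = 60.
- If 55 is fixed and the controls are the remainder: 55 − 30 = 25 to 55 − 35 = 20 controls, not 30.

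**Step 3: what the 50 implies.** No effect size is given, so the 50 cannot be derived. Worked backwards with the noncentral F distribution (λ = f² × N, denominator df = N − 8 − 1):

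- An overall test with 8 variables at N = 50 has 80% power for f² = 0.36 (R² = 0.265). Under assumed values, f² = 0.35 would need 52 subjects and f² = 0.15 would need 109.
- One coefficient at N = 50 has 80% power for f² = 0.165. If that coefficient is group, with equal groups and no correlation with the other variables, d = 2 × √0.165 = 0.81 SD.

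**Step 4: detectable group difference.** Two independent groups, common SD, no adjustment. The normal approximation is d = (1.960 + 0.842) × √(1/n₁ + 1/n₂). At 30 vs 30 it gives 2.802 × 0.258 = 0.72. The noncentral t distribution gives slightly larger values:

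| Robot vs historical | d for 80% power | Power for 0.5 SD |
|---|---|---|
| 25 vs 25 (total 50) | 0.81 | 41% |
| 30 vs 25 (total 55) | 0.77 | 44% |
| 35 vs 20 (total 55) | 0.80 | 42% |
| 30 vs 30 (total 60) | 0.74 | 48% |
| 35 vs 35 (total 70) | 0.68 | 54% |
| 27 vs 30 (10% robot drop-out, 30 × 0.90 = 27) | 0.76 | 46% |

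An assumed difference of 0.5 SD would need 64 per group.

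**Step 5: what a result could exclude.** This depends on the confidence interval, not on the detectable difference. At 30 vs 30 the expected 95% half-width is about 2.00 × √(2/30) = 0.52 SD.

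**Step 6: the floor of 20.** With 5 variables and N = 20, 80% power needs f² = 0.938 for the overall test, so R² = 0.938 / 1.938 = 0.48. For one coefficient it needs f² = 0.454, so partial r = √(0.454 / 1.454) = 0.56. The protocol gives no number to set against these.

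**The case against.** The best defence is that 55 is a minimum and 30 to 35 a recruitment target. Sixty then satisfies 55, and at about 30 robot patients the unquantified historical group agrees with the 30 in Section 1. The gap is then about five routine records. This is a possible reading, but Section 7.3 does not state it.

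A second defence is that group may be one of the independent variables, so the regression can cover the comparison. Step 3 supports this: under its conditions, N = 50 gives the same 0.81 SD as 25 vs 25. That answers whether the method is usable, but the figure is still absent from the protocol.

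Third, feasibility is the leading aim. That limits the weight of the point. The comparison nevertheless remains a stated aim, and the protocol chose to justify its numbers by power.

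A reader might also infer more than the documents support:

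- *That the 80% power claim for 20 subjects is false.* The strength of association is given only in words and the cited sources are not at hand. The claim is unsupported in the protocol, not shown to be wrong.
- *That the group comparison will be unadjusted and so biased by case-mix.* Section 7.2 plans no matching and Section 9 names no adjustment for this comparison, but Section 9 does not rule out regression. The model may stand in a statistical analysis plan that is not shown.
- *That no difference below 0.74 SD could be excluded.* This confuses power with precision: an observed difference near zero at 30 vs 30 would exclude differences beyond about 0.52 SD.

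**Conclusion.** The point holds as an inconsistency and an incomplete power statement, and it should be corrected. The protocol carries totals of 55, 60 and 60 to 70. The last figure assumes equal groups. The remainder reading of 55 conflicts with the 30 historical patients in Section 1.

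Across all the sizes the text allows, the detectable difference lies between about 0.68 and 0.81 SD, and power for 0.5 SD between 41% and 54%. These figures assume two-sided 5%, 80% power for the detectable difference, an approximately continuous outcome with a common SD, no adjustment, and data in both groups. The last condition matters: Section 8.3 lists the functional and sonographic examinations as study-related, whereas Section 8 takes historical data from routine records. Duration of ventilation may be the only primary outcome clearly available in both groups.

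I give no adjusted figure, because it would depend on a variance explained and a collinearity that the protocol does not state.

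**What to change.** **Needed**

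- Use one number per group in Sections 1 and 7.3, for example 30 robot and 30 historical patients, and correct the 55. Apply the 10% drop-out only to the prospective robot group, since retrospectively chosen controls do not drop out.
- State the detectable difference with its assumptions, for example:

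> With 30 vs 30 patients (27 vs 30 after 10% drop-out in the robot group), two-sided 5% and 80% power, an unadjusted comparison of an approximately continuous outcome available in both groups detects about 0.74 (0.76) SD; power for 0.5 SD is about 48% (46%). Results will be reported with 95% confidence intervals (expected half-width about 0.52 SD at 30 vs 30), and a non-significant result will not be read as no difference.

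- Give an adjusted figure only together with its assumed R² and variance inflation factor.

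**Optional**

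- Give the effect size behind the floor of 20 subjects, or delete that floor.
- If the statistical analysis plan does not already do so, name in Section 9 the regression that Section 7.3 is sized for as the group comparison. Group would be one variable, with a few pre-treatment covariates already collected, such as age and an admission severity score, in a form suited to each outcome. This reduces case-mix bias but does not remove it.

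**Cost.** Wording in Sections 1 and 7.3, and in Section 9 if the last option is taken, with a little more analysis. No robot patients are added. The stated power will look less favourable than the present text suggests.

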#### 7.4. TERMINATION CRITERIA FOR PATIENTS

All patients included in the study are free to withdraw their consent to participate in the study, in whole or in part, at any time and without giving reasons. In such a case, patients will be asked to state the reason for withdrawal but will be informed that they are not required to do so. Time and reasons for withdrawal (if given) will be documented. Patients can be excluded from the study if a violation of inclusion or exclusion criteria is subsequently determined or if the data collection is incomplete.

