#### *Exclusion criteria*

- Patients refusal to participate in the study
- unable to give informed consent
- chronically bedridden before inclusion
- clinical frailty scale  $\geq 7$  (42)
- chronic ventilation (more than 24 hours) before admission to the intensive care unit
- Elevated intracranial pressure / risk for elevated intracranial pressure / recent cerebral hemorrhage
- Pregnancy
- Pre-existing neuromuscular disease resulting in chronic limitation of strength and performance
- Sternotomy / Sternectomy during a surgical procedure

Patients meeting the following criteria will be retrospectively selected for the historical comparison group:

- planned surgical procedure
- Postoperative intensive care and therapeutic treatment
- Duration of ventilation > 48 hours
- age  $\geq 18$  years
- Weight >45 kg and <135 kg
- Body height >1.50 m and <1.95 m
- Patients who met any of the exclusion criteria during their intensive care unit stay will not be included in the historical group.

No matching is planned.

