#### 7.6. TERMINATION CRITERIA FOR THE ENTIRE STUDY

Termination of the study is not foreseen in general. An interim evaluation is not planned for short study durations.

If less than half of the patients have been recruited after three months, an interim evaluation will take place. The study can be discontinued if the interim evaluation shows that the recruitment rate is not sufficient to achieve the objectives mentioned under 4. as the number of patients is too low and an increase in the recruitment rate is not possible.

The decision to discontinue the study is made by the project management together with the study physicians. All patients included in the study up to the point of discontinuation should be evaluated in any case in order to be able to evaluate the early mobilization in this patient group, the previous implementation and the experience of the mobilizing specialists.

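### Protocol section 7.4 lets an included patient be excluded at discretion for incomplete data, with no definition and no duty to record when or why

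*Protocol*

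**What the plan says.** Section 7.4 (termination criteria for patients) gives two grounds on which the study team may remove a patient who is already included: "Patients can be excluded from the study if a violation of inclusion or exclusion criteria is subsequently determined or if the data collection is incomplete". It does not say which variables or visits make data collection incomplete, how much must be absent, who decides, or by when. For patients who withdraw consent, the same section requires that "Time and reasons for withdrawal (if given) will be documented". It asks for nothing comparable when the study team excludes a patient.

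Section 4.3 ties primary outcomes to the end of the ICU stay. Strength and function are surveyed with the MRC classification and "using the FSS-ICU (32, 33) at discharge ICU", and the muscle and diaphragm block ends with "Diaphragm mobility at discharge ICU". The third primary outcome, duration of invasive ventilation, does not depend on a discharge examination. Section 3.1 lists feasibility and adverse events as primary target criteria.

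Sections 8 and 8.3 place information and consent before surgery. Section 7.2 selects the historical group retrospectively and adds: "No matching is planned".

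Section 7.6 says: "All patients included in the study up to the point of discontinuation should be evaluated in any case". That sentence concerns a study that is stopped early.

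**The concern.** The clause acts on patients who are already in the study, and what triggers it is mostly learned after treatment has started. Instability, stopped treatment or possibly death in the ICU can each leave gaps in the discharge measures, and each may be related to outcome. If such patients are taken out, the robot group is partly defined by what happened under treatment. Neither randomisation nor matching is there to offset this.

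The exclusion is also from the study, not from one analysis. A patient without a discharge ultrasound could lose a recorded ventilation time and recorded adverse events as well, and might drop out of the feasibility counts. Because no time or reason need be recorded, a reader of the results could not tell whether any of this had happened.

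**Working it through.** **1. The texts side by side**

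| Question | Where | What is provided |
|---|---|---|
| May an included patient be removed for incomplete data? | 7.4 | Yes, permissively |
| Is incompleteness defined? | Nowhere in the protocol | No |
| Must time and reason be recorded? | 7.4 | For consent withdrawal only |
| Are discontinuations recorded? | 3.1, 8.1 | Weekly counts of discontinued interventions, premature termination per session, reasons for stopping robotic mobilization; not exclusions from the study |
| Must every included patient be evaluated? | 7.6 | Only if the whole study is stopped |

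Section 7.4 does not itself say that removal happens after treatment has begun. That is an inference from three facts: inclusion is preoperative, no time limit is set, and the measures most likely to be absent fall at ICU discharge.

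**2. The protocol's drop-out figure**

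The protocol gives no removal rate for this clause. The nearest figure is in section 7.3: "with an expected drop-out of 10%, 55 patients (robotic intervention and historical comparison group) should be included in the study". The base is 50.

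- 50 × 1.10 = 55, the stated figure.
- 50 / (1 − 0.10) = 55.6, so 56. The difference of one patient is immaterial here.
- Allowance: 55 − 50 = 5 patients, for all reasons and both groups.

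**3. Share of the robot group**

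Section 7.3 plans 30 to 35 robot patients.

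- Spread evenly: 0.10 × 30 = 3 and 0.10 × 35 = 3.5, a share of 0.10.
- All 5 in the robot group, since historical cases are picked afterwards from routine data: 5/35 = 0.14 and 5/30 = 0.17.

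**4. Shift of the robot-group mean**

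Let k of n patients be removed.

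- Mean of all = [(n − k) × mean kept + k × mean removed] / n.
- Hence mean kept − mean of all = (k/n) × (mean kept − mean removed).
- With k/n from 3/30 to 5/30, the factor is 0.10 to 0.17.

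For ventilation time this is 0.10 to 0.17 day for each day by which kept and removed patients differ. The protocol does not give that difference.

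**5. Illustration under assumptions that are not in the protocol**

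A simulation took 30 against 30 patients, no true effect, a t-test at two-sided 5%, and 3 of 30 removed from the robot group only. The correlation is between a poor outcome and being marked incomplete.

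| Correlation | Spurious benefit (SD) | Rejection rate |
|---|---|---|
| 0 | 0.00 | 4.9% |
| 0.3 | 0.06 | 5.4% |
| 0.5 | 0.09 | 7.0% |

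Removal does no harm to this comparison when incompleteness is unrelated to outcome, and the harm grows as the two become linked.

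**The case against.** **Death in the ICU may not count as incomplete.** Section 8 (robot-assisted early mobilization) lets a patient's study period end with death or with the end of the recording period. A patient who dies may thus have reached a planned end. This stands: the ICU-death route is plausible but not established. The same applies to 3-month follow-up, which section 8 makes conditional. A reader might infer that everyone without that visit is open to exclusion, but the text does not support this.

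**The feasibility counts may be safe.** Section 8.1 collects them as events occur, and no section says they are revised after an exclusion. This largely stands. A reader might infer that feasibility rates will be inflated; the documents support only that they could be, since nothing says an excluded patient stays in the counts.

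**An SAP may define analysis sets, and the clause may never be used.** Both are true, and how missing values are analysed can be left to an SAP. The point here is a rule that the protocol itself states. An SAP should not have to undo permission to remove a patient from the study.

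**The size is borrowed.** The 10% drop-out covers all reasons, and the upper end puts every loss in one group. This stands, so the figures are a scale and not an estimate.

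**A reader might also infer a bias in favour of the robot.** The document does not fix the direction. Removing a patient with a long unstable course would shorten mean ventilation time, while removing one who died early after short ventilation would lengthen it.

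**Conclusion.** The point holds as a badly fixed exclusion rule. The incompleteness ground is discretionary and undefined, and its use need not be recorded. Followed as written, it can select the robot group on post-treatment events in an unmatched comparison and discard outcomes that are available. The principle that everyone included is evaluated appears in section 7.6, but only for a study stopped early.

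The scale is a shift of 0.10 to 0.17 times the kept-minus-removed difference. It rests on the assumption that removals under this clause reach 3 to 5 of 30 robot patients. The documents do not show that such removals will occur, that deaths in the ICU will be among them, or which group would gain. The clause should be corrected; it does not by itself invalidate the study.

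**What to change.** In section 7.4:

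- Strike incomplete data collection as a ground for excluding a patient.
- State that included patients with incomplete data remain in the study, that their available data are analysed, and that they stay in the feasibility and adverse-event counts to which they belong.
- Require every exclusion to be documented and reported with its time and reason.

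Leave the eligibility-violation ground as it is, without a new time limit. Section 7.2 drops historical patients who met an exclusion criterion during their ICU stay, so a limit on the robot side alone would create a new asymmetry; reconciling the two is a separate point. Decisions on stopping treatment, and the handling of data after consent withdrawal (section 8.3), are unchanged.

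The cost is one paragraph of protocol wording and no extra data collection. Feasibility rates may look slightly less favourable, and missing values will have to be handled in the analysis.
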